5.10 Diet/Activity/Other Considerations

5.10.1 Diet

Subjects should maintain a normal diet unless modifications are required to manage an AE such as diarrhea, nausea or vomiting.

5.10.2 Contraception

Pembrolizumab may have adverse effects on a fetus in utero. Furthermore, it is not known if pembrolizumab has transient adverse effects on the composition of sperm. Non-pregnant, non-breast-feeding women may be enrolled if they are willing to use 2 methods of birth control or are considered highly unlikely to conceive. Highly unlikely to conceive is defined as 1) surgically sterilized, or 2) postmenopausal (a woman who is ≥ 45 years of age and has not had menses for greater than 1 year will be considered postmenopausal), or 3) not heterosexually active for the duration of the study. The two birth control methods can be either two barrier methods or a barrier method plus a hormonal method to prevent pregnancy. Subjects should start using birth control from study Visit 1 throughout the study period up to 120 days after the last dose of study therapy.

The following are considered adequate barrier methods of contraception: diaphragm, condom (by the partner), copper intrauterine device, sponge, or spermicide. Appropriate hormonal contraceptives will include any registered and marketed contraceptive agent that contains an estrogen and/or a progestational agent (including oral, subcutaneous, intrauterine, or intramuscular agents).

Subjects should be informed that taking the study medication may involve unknown risks to the fetus (unborn baby) if pregnancy were to occur during the study. In order to participate in the study they must adhere to the contraception requirement (described above) for the duration of the study and during the follow-up period defined in section 10.2.2-Reporting of Pregnancy and Lactation to the Sponsor and to Merck. If there is any question that a subject will not reliably comply with the requirements for contraception, that subject should not be entered into the study.

5.11 Duration of Follow up

The End of Treatment and Follow-up visit procedures are listed in Section 7 (Protocol Flow Chart) and Section 6.6.9 Visit Requirements). After the end of treatment, each subject will be followed for 30 days for adverse event monitoring (serious adverse events will be collected for 90 days after the end of treatment as described in Section 10.3). Subjects who discontinue for reasons other than progressive

disease will have post-treatment follow-up for disease status until disease progression, initiating a non-study cancer treatment, withdrawing consent or becoming lost to follow-up. After documented disease progression each subject will be followed by telephone for overall survival until death, withdrawal of consent, or the end of the study, whichever occurs first. The total study duration will be 3 years or until death of all participants.

5.11.1 Discontinuation of Study Therapy after CR

Discontinuation of treatment may be considered for subjects who have attained a confirmed CR that have been treated for at least 24 weeks with pembrolizumab and had at least two treatments with pembrolizumab beyond the date when the initial CR was declared. Subjects who then experience radiographic disease progression may be eligible for up to one year of additional treatment with pembrolizumab via the Second Course Phase at the discretion of the investigator if no cancer treatment was administered since the last dose of pembrolizumab, the subject meets the safety parameters listed in the Inclusion/Exclusion criteria, and the trial is open. Subjects will resume therapy at the same dose and schedule at the time of initial discontinuation. Additional details are provided in Section 6.6.9.6.

Participants will be followed for one year after removal from protocol therapy or until death, whichever occurs first. Participants removed from protocol therapy for unacceptable adverse event(s) will be followed until resolution or stabilization of the adverse event.

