5.9 Criteria for Taking a Participant Off Protocol Therapy

Duration of therapy will depend on individual response, evidence of disease progression and tolerance. In the absence of treatment delays due to adverse event(s), treatment with platinum + etoposide may continue for UP TO 6 TOTAL CYCLES (on and off therapy) but may be stopped at 4 cycles at investigator discretion based on tolerability. Treatment may be stopped at any time if one of the below criteria applies. Pembrolizumab may continue for up to 34 cycles (2 years) or until one of the following criteria applies:

- Disease progression
- Intercurrent illness that prevents further administration of treatment
- Unacceptable adverse event(s)
- Participant demonstrates an inability or unwillingness to comply with the oral medication regimen and/or documentation requirements
- Participant decides to withdraw from the protocol therapy
- General or specific changes in the participant's condition render the participant unacceptable for further treatment in the judgment of the treating investigator

Participants will be removed from the protocol therapy when any of these criteria apply UNLESS THERE IS ISOLATED CNS PROGRESSION (Section 5.11.2). The reason for removal from protocol therapy, and the date the participant was removed, must be documented in the case report form (CRF). Alternative care options will be discussed with the participant.

In the event of unusual or life-threatening complications, treating investigators must immediately notify the Overall PI, [name], [contact] .

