6.6.9.5 Survival Follow-up

Once a subject experiences confirmed disease progression or starts a new anti-cancer therapy, the subject moves into the survival follow-up phase and should be contacted by telephone every 12 weeks to assess for survival status until death, withdrawal of consent, or the end of the study, whichever occurs first.

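### Section 5.11.1 stops follow-up one year after protocol therapy while 5.11 and 6.6.9.5 follow survival to death or study end; if the one-year limit governs survival calls, OS beyond month 12 is overestimated

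*Combined protocol and SAP*

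**What the plan says.** Three places in the combined protocol and SAP set how long participants are followed.

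- **Section 5.11.1** (headed as concerning discontinuation after CR): "Participants will be followed for one year after removal from protocol therapy or until death, whichever occurs first". The next sentence reads: "Participants removed from protocol therapy for unacceptable adverse event(s) will be followed until resolution or stabilization of the adverse event".
- **Section 5.11**: "After documented disease progression each subject will be followed by telephone for overall survival until death, withdrawal of consent, or the end of the study". It also says: "The total study duration will be 3 years or until death of all participants".
- **Section 6.6.9.5**, the dedicated survival follow-up section: participants with confirmed progression or a new anti-cancer therapy are to be "contacted by telephone every 12 weeks to assess for survival status until death, withdrawal of consent, or the end of the study".

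Four other places bear on the point. Section 5.9 lists disease progression first among the reasons for stopping and adds: "Participants will be removed from the protocol therapy when any of these criteria apply", with an exception for isolated CNS progression. Section 5.7.1 gives only loss to follow-up, withdrawal of consent for data submission, and death as reasons for going off study. Section 8.1.6 censors OS at the date last known alive. Section 9.1 estimates OS by Kaplan-Meier and allows log-rank, Cox and landmark analyses.

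**The concern.** A site could stop survival calls 12 months after a participant leaves therapy and cite 5.11.1. It could equally continue to death or study end and cite 5.11 or 6.6.9.5.

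If the one-year limit is applied to survival calls, a participant's OS censoring time is fixed by when therapy ended. Progression is a principal reason for removal, so participants who progress early are censored early while those still on drug stay at risk. Kaplan-Meier, log-rank and Cox methods all assume that censoring carries no information about prognosis. Here it would.

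What is at stake is OS after the first year: the tail of the curve, and any comparison that draws on it. OS is a secondary endpoint. With 15 participants planned per cohort, late deaths are few, and calls stopped at some sites but not others would be hard to repair afterwards.

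**Working it through.** The plan states no OS event count, power or late-OS estimate, so there is no figure of its own to reproduce on this point. Its only power statement (Section 9.1) concerns paired biopsies and does not depend on follow-up.

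**Step 1. When the limit would censor.** Let R be the time from registration to removal from protocol therapy. The limit gives C = R + 12 months.

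- Removed at once: C = 0 + 12 = 12, the earliest possible.
- Removed at month 2: C = 2 + 12 = 14.
- Removed at month 20: C = 20 + 12 = 32.
- Removed at month 24, the 2-year treatment maximum: C = 24 + 12 = 36.

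No estimate up to month 12 can change. At a later month t, only participants removed after month t − 12 are still at risk. At month 24 these are the participants whose therapy lasted at least 12 months.

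**Step 2. Inputs for size.**

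- From the plan: historical median PFS 5.4 months and median OS 9.5 months (Section 3.3), treatment up to 2 years (Section 5.9), study duration 3 years (Section 5.11), Kaplan-Meier (Section 9.1).
- Assumed: administrative limit at 36 months from registration; removal at R = min(PFS, 24); OS = PFS + post-progression survival (PPS); exponential times; the dependence between PFS and PPS; and median OS values above 9.5 months.

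**Step 3. Calculation.** Large simulated samples (200,000 to 400,000 participants) compare censoring at 36 months only with censoring at min(R + 12, 36). Two families were used:

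- *Copula:* PFS median 5.4 months; PPS independent of PFS, or linked to it by a Gaussian copula with ρ = 0.5.
- *Frailty:* gamma frailty (variance 0.5) shared by PFS (base median 5.4) and PPS (base medians 4 and 6). The frailty raises the realised median PFS to about 6.5 months.

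| Model | Median OS (months) | 24-month OS, full follow-up | 24-month OS, one-year limit | Bias (points) | Deaths within 36 months lost | Censored by the limit before month 36 |
|---|---|---|---|---|---|---|
| Independent | 9.5 | 8.8% | 9.7% | +0.8 | 4.0% | 4.1% |
| ρ = 0.5 | 9.5 | 12.9% | 13.9% | +1.0 | 5.2% | 5.9% |
| Independent | 14 | 21.9% | 24.8% | +2.9 | 21.8% | 24.8% |
| ρ = 0.5 | 14 | 26.7% | 31.5% | +4.9 | 22.9% | 28.2% |
| Frailty | about 13.6 | 29.8% | 32.4% | +2.6 | about 13% | about 16% |
| Frailty | about 16.5 | 36.2% | 40.0% | +3.8 | about 20% | about 25% |

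(Biases are taken before rounding.) The direction is upward in every row. In the two 14-month rows the gap keeps widening: 36-month OS is about 7% against 11% (independent) and 12% against 22% (ρ = 0.5).

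**Step 4. The planned summaries.** Section 2.2 asks for median OS and 6-month OS.

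- 6-month and 12-month OS: identical under both rules in every scenario.
- Median of 9.5 months: identical.
- Median of 14.0 months: reads 14.1.
- Median of about 16.5 months: reads about 0.5 month higher.

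**Step 5. Comparison with sampling error.** For a 30% survival estimate before any censoring, SE = √(0.3 × 0.7 / n). With n = 60 this is 5.9 points; with n = 15 it is 11.8 points. The 24-month bias is smaller than either.

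**The case against.** The strongest reply is that the sentence is a stray. It sits under a CR heading and never mentions survival, while every section that governs survival is uncapped: 5.11, 6.6.9.5, the off-study list in 5.7.1 and the censoring rule in 8.1.6. If it covers only CR stoppers, it would shorten follow-up for the best responders, and the link to early failure disappears. This stands as a real ambiguity, but it does not remove the conflict. The sentence speaks of participants without qualification, uses the same idea of removal from protocol therapy as 5.9, and is followed by a sentence on adverse-event removals that has nothing to do with CR. The general reading is the more natural one. On the narrow reading, a CR stopper who later progresses still has two different follow-up periods.

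Three stronger readings are tempting, and the documents do not support them.

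- *A reader might infer that the plan's OS results will be biased.* That follows only if the limit is applied to survival calls, and the sections written for survival say otherwise.
- *A reader might count everyone whose follow-up ends under the limit as lost to it*: 29% and 39% in the two frailty scenarios. These totals include participants whose limit falls at month 36, where a 36-month study end would stop follow-up anyway. Censoring before month 36 is about 16% and 25%; the difference (29 − 16 = 13 and 39 − 25 = 14 points) is not a cost of the contradiction. If the 3 years run from first enrolment, the cost is smaller still.
- *A reader might say that the limit undermines the trial's stated purpose of durable survival.* The rationale (Section 1.6) centres on PD-L1 variability and the timing of checkpoint inhibition. Durability appears as background in Section 1.1.1, and 24-month OS is not a planned summary.

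It is also fair to say that the one OS figure the plan uses as its comparator is 9.5 months, where the 24-month bias is about 1 point, and that even the larger biases lie within sampling error.

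**Conclusion.** The contradiction stands: one sentence ends follow-up a year after therapy, two sections run survival follow-up to death, withdrawal of consent or study end, and nothing decides between them.

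If the limit is applied to survival calls for all participants, OS censoring depends on prognosis and Kaplan-Meier OS after month 12 is too high. The size at 24 months is about +1 point with median OS near 9.5 months (about 5% of deaths within 36 months lost). It is about +3 to +5 points with median OS of about 14 to 16 months (about 13% to 23% of deaths lost). If the limit applies only to CR stoppers, the conflict remains without the link to early failure.

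These sizes rest on the assumed relation between PFS and post-progression survival, on removal at progression or 24 months, and on a 36-month limit from registration. The direction and the absence of any effect up to month 12 do not depend on the correlation chosen.

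The 6-month OS and the primary PD-L1 endpoint are unaffected. Median OS is unaffected below 12 months and moves little above it. This is a minor point, worth correcting because the correction is easy.

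**What to change.** Delete the one-year sentence in Section 5.11.1, or limit it expressly to clinic follow-up. State once that survival follow-up for all participants, whatever the reason for leaving therapy, runs until death, withdrawal of consent or study end, with the 12-weekly calls of Section 6.6.9.5, and align the OS censoring text in Section 8.1.6 with it.

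Deletion is the simpler choice. The disease-status follow-up in 5.11 and 6.6.9.4 for participants who stop without progression also carries no one-year limit, so a sentence kept for clinic follow-up would have to be reconciled with those sections too.

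The cost is one sentence in the next amendment. The calls are already scheduled, so no new procedure is needed.

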5.11.2 Treatment beyond isolated CNS progression

If there is isolated CNS progression for which participants may be treated with radiation (i.e. participants who did not receive PCI but then experienced isolated CNS progression), treatment with pembrolizumab may be continued following radiation.

Radiation should commence no less than 2 weeks and no more than 4 weeks from the last dose of pembrolizumab. Pembrolizumab should be restarted no less than 2 weeks and no more than 6 weeks after completion of radiation.

5.12 Ordering

Each individual site will be responsible for ordering and maintaining drug supply of pembrolizumab from Merck, Sharp, and Dohme.

5.13 Receiving, Storage, Dispensing and Return

5.13.1 Accountability

The investigator, or a responsible party designated by the investigator, should maintain a careful record of the inventory and disposition of the agent using the NCI Drug Accountability Record Form (DARF) or another comparable drug accountability form. (See the NCI Investigator's Handbook for Procedures for Drug Accountability and Storage.)

5.13.2 Receipt of Drug Supplies

The investigator shall take responsibility for and shall take all steps to maintain appropriate records and ensure appropriate supply, storage, handling, distribution and usage of investigational product in accordance with the protocol and any applicable laws and regulations. Clinical Supplies will be provided by Merck as summarized in Table 7.

Table 7 Product Descriptions

Product Name & Potency	Dosage Form
Pembrolizumab 100 mg/ 4mL	Solution for Injection

Upon receipt of the of the study treatment supplies, an inventory must be performed and a drug receipt log filled out and signed by the person accepting the shipment. It is important that the designated study staff counts and verifies that the shipment contains all the items noted in the shipment inventory. Any damaged or unusable study drug in a given shipment (active drug or comparator) will be documented in the study files. The investigator must notify study sponsor of any damaged or unusable study treatments that were supplied to the investigator's site.

5.13.3 Storage and Stability

Clinical supplies must be stored in a secure, limited-access location under the storage conditions specified on the label for each drug.

Receipt and dispensing of trial medication must be recorded by an authorized person at the trial site.

Clinical supplies may not be used for any purpose other than that stated in the protocol.

5.13.3.1 Compatibility

- The following infusion set materials are compatible with pembrolizumab (MK-3475):
 - PVC Infusion set that is plasticized using DEHP
 - PVC and tri-(2-ethylhexyl) trimellitate (TOTM) infusion set
 - Polyethylene lined PVC infusion set
 - PVC Infusion set that is plasticized using Di-2-ethylhexyl Terephthalate (DEHT)
 - Polyurethane set

*Contact Sponsor for materials not listed above

5.13.4 Dispensing of Study Drug

5.13.4.1 Handling

Qualified personnel, familiar with procedures that minimize undue exposure to themselves and the environment, should undertake the preparation, handling, and safe disposal of the chemotherapeutic agent in a self-contained and protective environment.

Pembrolizumab (MK-3475) Powder for Solution for Infusion vials should be stored at refrigerated conditions (2 – 8 °C). Prior to reconstitution, the vial of lyophilized powder can be out of refrigeration (temperatures at or below 25°C (77°F)) for up to 24 hours. Refer to pharmacy manual for further details.

5.13.5 Return or Destruction of Study Drug

Unused pembrolizumab (MK-3475) Powder for Solution for Infusion or Solution for Infusion vial(s) shall be returned to the designated facility for destruction.

- For US clinical sites, return to: Fisher Clinical Services, Return and Destruction Center, [name]

Solution remaining in a used vial should be discarded as Chemotherapeutic Waste according to local procedures of the institution.

At the completion of the study, there will be a final reconciliation of drug shipped, drug consumed, and drug remaining. This reconciliation will be logged on the drug reconciliation form, signed and dated. Any discrepancies noted will be investigated, resolved, and documented prior to return or destruction of unused study drug. Drug destroyed on site will be documented in the study files.

5.14 Standard Agents

Cisplatin, carboplatin, and etoposide will be purchased commercially as they are for standard of care. Storage, handling, administration, accounting, and destruction will be as per institutional standards.

6 Study Procedures

The Trial Flow Chart - Section 7 summarizes the trial procedures to be performed at each visit. Individual trial procedures are described in detail below. It may be necessary to perform these procedures at unscheduled time points if deemed clinically necessary by the investigator.

Furthermore, additional evaluations/testing may be deemed necessary by the Sponsor and/or Merck for reasons related to subject safety. In some cases, such evaluation/testing may be potentially sensitive in nature (e.g., HIV, Hepatitis C, etc.), and thus local regulations may require that additional informed consent be obtained from the subject. In these cases, such evaluations/testing will be performed in accordance with those regulations.

6.1 General Informed Consent

Consent must be documented by the subject's dated signature or by the subject's legally acceptable representative's dated signature on a consent form along with the dated signature of the person conducting the consent discussion.

A copy of the signed and dated consent form should be given to the subject before participation in the trial.

The initial informed consent form, any subsequent revised written informed consent form and any written information provided to the subject must receive the NYU IRB's approval in advance of use. The subject or his/her legally acceptable representative should be informed in a timely manner if new information becomes available that may be relevant to the subject's willingness to continue participation in the trial. The communication of this information will be provided and documented via a revised consent form or addendum to the original consent form that captures the subject's dated signature or by the subject's legally acceptable representative's dated signature.

Specifics about a trial and the trial population will be added to the consent form template at the protocol level.

The informed consent will adhere to NYU IRB requirements, applicable laws and regulations.

6.2 Inclusion/Exclusion Criteria

All inclusion and exclusion criteria will be reviewed by the investigator and qualified designee to ensure that the subject qualifies for the trial.

6.3 Medical History

A medical history will be obtained by the investigator or qualified designee. Medical history will include all active conditions, and any condition diagnosed within the prior 10 years that are considered to be clinically significant by the Investigator. Details regarding the disease for which the subject has enrolled in this study will be recorded separately and not listed as medical history.

6.4 Prior and Concomitant Medication Review

6.4.1 Prior Medications

The investigator or qualified designee will review prior medication use, including any protocol-specified washout requirement, and record prior medication taken by the subject within 28 days before starting the trial. Treatment for the disease for which the subject has enrolled in this study will be recorded separately and not listed as a prior medication.

6.4.2 Concomitant Medications

The investigator or qualified designee will record medication, if any, taken by the subject during the trial. All medications related to reportable SAEs should be recorded as defined in Section 10.3

6.4.3 Prior chemotherapy

The investigator or qualified designee will record all chemotherapy cycles and doses given prior to study entry as well as reported response to prior therapy. For cohort C, CT scan to assess initial response will be collected and evaluated by RECIST 1.1 criteria as for scans ON-STUDY and recorded in screening documentation.

6.5 Disease Details

The investigator or qualified designee will obtain prior and current details regarding disease status.

